## STATEMENT OF COMPLIANCE

This protocol describes the FluSHED-2 study and provides information about procedures for entering participants. The protocol should not be used as a guide for the treatment of other participants; every care was taken in its drafting, but corrections or amendments may be necessary. These will be circulated to investigators in the study, but centres entering participants for the first time are advised to contact the trials centre to confirm they have the most recent version.

Problems relating to this trial should be referred, in the first instance, to the study coordination centre.

This trial will adhere to the principles outlined in the Medicines for Human Use (Clinical Trials) Regulations 2004 (SI 2004/1031), amended regulations (SI 2006/1928) and the International Conference on Harmonisation Good Clinical Practice (ICH GCP) guidelines. It will be conducted in compliance with the protocol, the Data Protection Act and other regulatory requirements as appropriate.

## PROTOCOL SYNOPSIS

Title	Assessment of daily viral shedding in the week following administration of live attenuated influenza vaccine in children: Flu-shed-2 study
Abbreviated title	Flu-shed 2
Eudra CT registration no.	2018-002470-42
HRA NRES Number	18/LO/1317
Sponsor R&D Number	18SM4658
Clinicaltrials.gov no.	NCT03735147
HRA IRAS reference	250312
Primary objective	To measure kinetics of type-specific vaccine virus shedding in 2018/19 following LAIV administration.
Intervention and key procedures	
Single dose of intranasal LAIV.
 
A blood sample, oral fluid sample and nasal swab will be collected pre- and 4 weeks after vaccination.
 
Daily nasal swab (collected by parent) for the week following vaccination.
 
(To fulfil a duty of care, influenza vaccine-naïve individuals under 9 years of age AND at high risk for influenza infection will be eligible for a second dose 4 weeks later, as per Department of Health /PHE guidelines).

Safety	Participants will be immunised in hospital by qualified staff, and observed for at least 20 minutes following a dose.
Patient group	Children (age 6-15 years) who are eligible (according to current UK guidance) to receive LAIV and who are attending a paediatric facility at St Mary's Hospital, London. Target recruitment of 30 subjects.
Primary outcome	To measure type-specific vaccine virus shedding in 2018/19 and how this varies in the 8 days following vaccination.
Secondary outcomes	Quantitative analysis of immunogenicity using a range of indicators (including HI and/or MN, and nasal IgA responses), and to measure the association between type-specific vaccine immunogenicity and virus shedding.
Sponsor	Imperial College London
Funding	NIHR HPRU in Respiratory Infections at Imperial College London MRC grant to [name], Imperial College London

## Funding

NIHR HPRU in Respiratory Infections at Imperial College London, with further mechanistic assessments funded through a Medical Research Council grant (reference MR/K010468/1) to [name], Imperial College London.

This protocol describes the FluSHED-2 study and provides information about procedures for entering participants. The protocol should not be used as a guide for the treatment of other participants; every care was taken in its drafting, but corrections or amendments may be necessary.

Problems relating to this trial should be referred, in the first instance, to the study centre.

This trial will adhere to the principles outlined in the Medicines for Human Use (Clinical Trials) Regulations 2004 (SI 2004/1031), amended regulations (SI 2006/1928) and the International Conference on Harmonisation Good Clinical Practice (ICH GCP) guidelines. It will be conducted in compliance with the protocol, the Data Protection Act and other regulatory requirements as appropriate.

**LIST OF ABBREVIATIONS**

AE	Adverse Event
CI	Chief Investigator
CMI	Cell mediated immunity
CRF	Case Report Form
CTA	Clinical Trial Authorisation
ELISA	Enzyme-linked Immunosorbent Assay
GCP	Good Clinical Practice
ICH	International Conference on Harmonisation
IRAS	Integrated Research Application System
µg	Micrograms
MHRA	Medicines and Healthcare products Regulatory Agency
NHS	National Health Service
NRES	National Research Ethics Service
PHE	Public Health England
PIL	Parent Information Leaflet
SAE	Serious Adverse Event
SOP	Standard Operating Procedure
SPC	Summary of Product Characteristics
SUSAR	Suspected Unexpected Serious Adverse Reaction

## 1. INTRODUCTION

### 1.1 BACKGROUND

LAIV was introduced into the UK immunisation schedule for children in 2013/14, and Public Health England has since been closely monitoring programme performance. In 2015/16, the UK found evidence of significant effectiveness of LAIV against laboratory confirmed influenza in both primary and secondary care including against A/H1N1pdm09. The UK results concord with those from several other geographical settings, although a number of studies report relatively lower effectiveness of LAIV against A/H1N1pdm09 infection compared to inactivated influenza vaccine (IIV). The reasons for these apparent differences in effectiveness are currently unclear.

Despite a suspension of the paediatric immunisation programme in 2017/18 mainly due to poor efficacy measures in previous years, the USA Advisory Committee on Immunisation Practice (ACIP) has reinstated its routine programme for the winter of 2018/19.

Several hypotheses are emerging to explain the apparent reduction in A/H1N1pdm09 quadrivalent LAIV effectiveness in the USA last season and their discordance with findings elsewhere including the UK together with the possible lower effectiveness of LAIV against A/H1N1pdm09 compared to IIV. These include one or more of the following:

1. CDC/DoD specific finding – related to chance, methodology, programmatic issues
2. Reduced replicative fitness of the current A/H1N1pdm09 strain.
3. Viral interference/competition between A/H1N1pdm09 vaccine strain and other vaccine viruses in multivalent formulation;
4. Prior vaccination with LAIV or IIV resulting in specific immunological interference with H1N1pdm09 vaccine virus replication;
5. Repeat LAIV vaccination resulting in broader, longer term immunological changes affecting all viruses (mimicking adult response);
6. Combinations of the above

Based upon in vitro studies, the manufacturer of LAIV (MedImmune) have stated that reduced replicative fitness of the A/H1N1pdm09 strain is likely to be the important root cause. However, this factor alone cannot explain the difference in effectiveness observed between the USA and sites elsewhere including the UK. This suggests that there is an important additional factor(s) involved. The US programme has been running for many more years than the UK – and in addition children 6 months to 24 months of age are offered IIV, unlike the UK. These prior vaccine exposures are potential contributory factors, which is currently being analysed by a group at Public Health England from a study conducted in 2017/18 for which [name] was CI.

LAIV shedding studies in children could be an important way to confirm whether impediments to viral replication do indeed explain these observed reductions in VE and what future implications (if any) this might have for the UK paediatric LAIV programme. LAIV virus replication in children will be dependent on virological and host factors. The virus factors include replicative fitness of individual strains and the

susceptibility to inhibition by other replicating strains (ability to compete). Host factors which may influence this include pre-existing specific immunity as a result of prior infection or previous vaccination (with either LAIV or IIV), and innate immune factors including mucosal immunity.

There is significant variability in shedding across viral subtypes in studies done to date, so there is a need to obtain local data in a small pilot observational study which will look in detail at virus shedding by sequential daily virus samples, something not possible on a larger scale. The data generated will inform future LAIV studies in the UK in terms of optimum time of sample collection for viral shedding studies, which are likely to be required on a regular basis, to supplement field studies of vaccine effectiveness. Obtaining additional samples (blood, oral fluids, nasal swabs) which are correlates of vaccine take will allow us to measure the association between type-specific vaccine immunogenicity and virus shedding and will add to existing data from previous seasons on this.

## 1.2 RESEARCH QUESTION

To measure type-specific vaccine virus shedding by sequential daily virus samples, and assess how this relates to immunogenicity in the 2018/19 vaccination season.

This study will enrol up to 30 children that will allow these factors to be assessed. Both written informed consent from parent/ guardian and written assent from the child will be in place prior to any study procedure. All participants will have a baseline assessment of pre-existing influenza immunity (blood test, oral fluid collection and nasal swabs), followed by a single dose of LAIV. Parents will then be asked to take nasal swabs at home on days 1, 2, 3, 4, 5, 6, 7, 8, with further nasal swab, blood test and oral fluid collection in hospital 4 weeks later, in order to assess for immune responses to LAIV.

## 2. STUDY OBJECTIVES

### 2.1 PRIMARY OBJECTIVE

To measure kinetics of type-specific vaccine virus shedding in 2018/19 in the eight days following LAIV administration.

### 2.2 SECONDARY OBJECTIVE

Quantitative analysis of immunogenicity using a range of indicators (including HI and/or MN, and nasal IgA responses), and to measure the association between type-specific vaccine immunogenicity and virus shedding.

### 3. STUDY DESIGN

- Type of Study:** Single centre, interventional study of the virus shedding in children receiving LAIV
- Number of Subjects:** 30
- Expected Duration:** Influenza vaccine season (estimated to commence September 2018 (exact date depending on availability of the Fluenz vaccine from UK Department of Health)).

### 4. STUDY POPULATION

This is a single group study, no randomisation, in children aged 6-15 years at enrolment.

#### 4.1 RECRUITMENT

Subjects will be recruited from existing paediatric services at St Mary's Hospital, London. Recruitment will be via publicity (posters, flyers), email and postal mailing (with an option for a follow-up contact by post, email or telephone\* where there is no response to the initial invite).

\*Telephone calling will only take place where the child/family is already under the care of the local clinical team, and the clinician thus has an established relationship with the family.

#### 4.2 ELIGIBILITY CRITERIA: CHILDREN TO RECEIVE LAIV

##### 4.2.1 INCLUSION CRITERIA

1. Children age 6 years to 15 years +364 days of age on enrolment
2. Children eligible to receive LAIV in accordance with Green Book advice  
[\[https://www.gov.uk/government/organisations/public-health-england/series/immunisation-against-infectious-disease-the-green-book\]](https://www.gov.uk/government/organisations/public-health-england/series/immunisation-against-infectious-disease-the-green-book)
3. Written informed consent given by parent/ guardian and assent from child (both must be in place to proceed).

##### 4.2.2 EXCLUSION CRITERIA

1. **Contraindications to LAIV** (notwithstanding allergy to egg protein), which include:
  - a. Hypersensitivity to the active ingredients, gelatin or gentamicin (a possible trace residue)
  - b. Previous systemic allergic reaction to LAIV
  - c. Previous allergic reaction to an influenza vaccine (not LAIV) is a relative contra-indication, which must be discussed with the CI to confirm patient suitability

- d. Children/adolescents who are clinically immunodeficient due to conditions or immunosuppressive therapy such as: acute and chronic leukaemias; lymphoma; symptomatic HIV infection; cellular immune deficiencies; and high-dose corticosteroids\*.

\***High-dose steroids** is defined as a treatment course for at least one month, equivalent to a dose *greater than* 20mg prednisolone per day (any age), or for children under 20kg, a dose *greater than* 1mg/kg/day.

NB: LAIV is not contraindicated for use in individuals with asymptomatic HIV infection; or individuals who are receiving topical/inhaled/low-dose oral systemic corticosteroids or those receiving corticosteroids as replacement therapy, e.g. for adrenal insufficiency.

- e. Children / adolescents younger than 18 years of age receiving salicylate therapy because of the association of Reye's syndrome with salicylates and wild-type influenza infection.
- f. Pregnancy (determined by history). Where this cannot be confirmed, a urine pregnancy test will be performed.

#### 4.3 SUBJECT WITHDRAWAL

Parents/guardians may withdraw their child at any time without giving a reason. In accordance with the current revision of the Declaration of Helsinki and any other applicable regulations, the parents or legal representatives of the child have the right to withdraw the participant from the study at any time and for any reason, without prejudice to his or her future medical care, and are not obliged to give his or her reasons for doing so.

The investigator may withdraw a participant from the study at any time if, in the investigator's clinical judgment, it is in the best interests of the participant's health and well-being. In addition the participant may be withdrawn for any of the following reasons:

- Decision by the Investigator
- Ineligibility (either newly arising during the study, or retrospective having been overlooked at screening)
- Significant protocol deviation
- Participant non-compliance with study requirements
- An adverse event which requires discontinuation of the study treatment, or results in inability to continue to comply with study procedures.

If known, the reason for withdrawal should be recorded in a CRF. If the participant is withdrawn due to an adverse event, the Investigator will arrange for appropriate follow-up through telephone calls (and/or visits if necessary) until the adverse event has resolved or stabilised.

All safety data for any participants withdrawn after receiving the study vaccination will be included in the data analyses, unless specific instruction for their destruction is received from the participant or their parent/guardian. Withdrawn participants will not be replaced.

## 5. STUDY TREATMENT

### 5.1 DESCRIPTION

Live Attenuated Intranasal Vaccine (LAIV) Quadrivalent vaccine (Fluenz-Tetra, Astra Zeneca), as provided for use by the Department of Health as part of the UK National Immunisation Schedule

### 5.2 DOSAGE AND ROUTE OF ADMINISTRATION

0.2 ml (administered as 0.1 ml per nostril). Immunisation will be carried out by nasal administration, as per the SmPC provided.

### 5.3 DOSE MODIFICATION

[figure not shown]
No dose modification proposed.

[figure not shown]
[figure not shown]
[figure not shown]
[figure not shown]
[figure not shown]
[figure not shown]
### 5.4 PREPARATION AND ADMINISTRATION OF STUDY DRUG

FLUENZ IS FOR NASAL USE only.

- DO NOT USE WITH A NEEDLE. Do not inject.
- FLUENZ is administered as a divided dose in both nostrils.
- After administering half of the dose in one nostril, administer the other half of the dose in the other nostril immediately or shortly thereafter.
- The patient can breathe normally while the vaccine is being administered – there is no need to actively inhale or sniff.
- Refer to the FLUENZ administration diagram (Figure 2) for step-by-step administration instructions.

**Figure 2 FLUENZ Administration**

		
1 Check expiry date Product must be used before date on applicator label.	2 Prepare the applicator Remove rubber tip protector. Do not remove dose-divider clip at the other end of the applicator.	3 Position the applicator With the patient in an upright position, place the tip just inside the nostril to ensure Fluenz is delivered into the nose.
		
4 Depress the plunger With a single motion, depress plunger as rapidly as possible until the dose-divider clip prevents you from going further.	5 Remove dose-divider clip For administration in the other nostril, pinch and remove the dose-divider clip from plunger.	6 Spray in other nostril Place the tip just inside the other nostril and with a single motion, depress plunger as rapidly as possible to deliver remaining vaccine.

Any unused product will be disposed of in accordance with local requirements for medical waste.

## 5.5 DISPENSING AND PRODUCT ACCOUNTABILITY

Fluenz Tetra (quadrivalent LAIV) is approved by the European Medicines Agency and distribution and administration to selected children will take place during the influenza season 2018-19. Provision of doses of vaccine will be through the Department of Health vaccine supply network as part of the national immunisation programme, with no additional requirements (e.g. cold chain monitoring) beyond that provided by the normal UK vaccine supply system. Vaccine will be delivered via existing systems to on-site pharmacists at study sites (all NHS hospitals). Vaccine doses will be dispensed from hospital stock as standard of care with no additional labelling required, as this is a type A Phase IV study. Doses will be released according to local procedure, using existing hospital systems and logging (rather than CTIMP-specific documentation).

## 6 STUDY VISITS & PROCEDURES

The study schedule is summarised in the following flow chart and table:

	Visit 1	Days 1,2,3,4,5,6,7,8	Visit 2 - Day 28 (window D21-42)
Written Informed Consent (parent/guardian)	x		
Written assent (child)	x		
Medical assessment	x		
Urine pregnancy test (if pregnancy cannot be excluded by clinical history alone)	x		
Vaccine administration followed by 20 mins observation	x		
Nasal swab and adverse event form	x	x (at home)	x
Oral fluid collection	x		x
Blood test	x §		x
2 nd dose in children <9 years who meet DoH criteria (see 6.1.3)			(x)

§baseline blood sample may be collected up to 2 months before vaccination, if the study participant is having a blood test for another reason and informed consent has been obtained already.

Both study visits will be carried out by members of the research team as per the above schedule, and appointment windows. If any SAE is reported, this will be documented following routine procedures. All clinical information and agreement with parents to be documented in CRFs.

### 6.1 STUDY VISITS / HOME INTERVENTIONS

#### 6.1.1 VISIT 1 - DAY 0

- Answer any questions the family has about the study having read the PIL.
- Obtain written informed consent from the parent/guardian
- Obtain written assent from child
- Verify inclusion and exclusion criteria with the parent/ guardian (if any notes need to be checked this would be done after consent)
- If the child meets all the inclusion criteria and none of the exclusion criteria, enrol in the study and allocate the next sequential unique participant study number.
- Measure and record body temperature
- *Collect baseline blood sample (up to 25ml). Participants will be offered local anaesthetic cream (to be applied 30mins prior to venepuncture) to minimise discomfort.§*
- Take the initial nasal swab, demonstrating to parents how this is done to facilitate compliance with taking the nasal swabs at home in the 8 days following vaccination.
- Administer LAIV according to prescription chart, and record this on CRF and chart, including batch number and expiry.
- Observe for 20 minutes, during which time collect oral fluid sample. Also confirm parent has understood how to take the nasal swabs, including posting back to team.
- Record vaccination details via the medical records system.
- Ask parent/ guardian to notify study team of any serious adverse events/reactions
- Arrange further visit for 3-6 weeks following vaccination.

§baseline blood sample may be collected up to 2 months before vaccination, if the study participant is having a blood test for another reason and informed consent has been obtained already.

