#### **Oral fluid samples:**

The first oral fluid sample will be collected by the nurse at the day 0 appointment, the second at Visit 2. The procedure involves passing a foam tipped swab across the teeth and gum line for around a minute in an action similar to brushing teeth.

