### Oral fluid

All oral fluid samples will be analysed by ELISA using plates coated with antigens specific for the viruses in the vaccine. This will initially be limited to detection of IgG antibody to A/California/7/2009 (antigenically similar to A/Michigan/45/2015 (H1N1)pdm09-like virus, and include detection of antibody specific for H3N2 virus antigenically like the A/Hong Kong/4801/2014 (H3N2)-like virus, B/Brisbane/60/2008-like virus and a B/Phuket/3073/2013-like virus, once these tests have been developed and validated). The method uses the recombinant HA1 fragment of haemagglutinin from each individual vaccine virus for coating 96 well plates, onto which strain specific antibodies, present in oral fluid samples bind. This bound antibody is initially complexed with biotin-labelled anti-human IgG, followed by its detection using streptavidin-HRP conjugate to enhance detection. Each oral fluid is analysed in triplicate in 1:50 dilution. The results will be reported as T/N ratio (OD sample/OD negative control).

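### The day 0 oral fluid sample is scheduled after the LAIV dose, although the synopsis and section 1.2 make it a pre-vaccination baseline

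*Combined protocol and SAP*

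**What the plan says.** Two places set the intended timing. The synopsis states: "A blood sample, oral fluid sample and nasal swab will be collected pre- and 4 weeks after vaccination". Section 1.2 describes a "baseline assessment of pre-existing influenza immunity (blood test, oral fluid collection and nasal swabs), followed by a single dose of LAIV". In both, oral fluid comes before the dose.

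Section 6.1.1, the working list for Visit 1, has a different order. Baseline blood and the initial nasal swab come first, then "Administer LAIV according to prescription chart, and record this on CRF and chart, including batch number and expiry", and then "Observe for 20 minutes, during which time collect oral fluid sample". The schedule table in section 6 confirms which side of the dose the 20 minutes fall on: "Vaccine administration followed by 20 mins observation".

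Section 6.3.1 does not settle the matter. It says "The first oral fluid sample will be collected by the nurse at the day 0 appointment, the second at Visit 2", which fits either order.

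On the assay, section 6.4 describes an ELISA on plates coated with the recombinant HA1 fragment from each vaccine virus, reported as a T/N ratio. On scope it says "This will initially be limited to detection of IgG antibody to A/California/7/2009", with the other three strains to follow once those tests are developed and validated. Section 9.1.2 lists oral fluid among the secondary outcomes as data equivalent to the serum titres, whose item includes day 28/day 0 ratios.

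**The concern.** A baseline value should be collected under the conditions that the protocol states, and under the same conditions as the follow-up value with which it is compared. Here the working checklist departs from the stated design, so staff who follow it will not deliver the sample that the synopsis promises.

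The departure also makes the two oral fluid samples unlike each other. The day 0 sample comes minutes after vaccine has been sprayed into both nostrils. At Visit 2 (section 6.1.3) the oral fluid is listed before any second dose. If vaccine liquid reached the mouth, it could dilute the day 0 sample or supply antigen that competes with the coated HA1 for antibody. Any such effect would fall on the day 0 value alone, which is the natural denominator of the oral fluid day 28/day 0 comparison. Because 6.1.1 schedules every child in the same way, there would be no unaffected children for comparison.

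**Working it through.** The documents give no figure to reproduce. The check sets side by side each place that fixes the timing or use of the sample.

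| Place | Timing of the day 0 oral fluid sample |
|---|---|
| Synopsis | Before vaccination |
| Section 1.2 | Part of the baseline assessment, then the dose |
| Section 6, schedule table | Visit 1; the 20-minute observation follows the vaccine |
| Section 6.1.1 | Inside the 20-minute observation, so after the dose |
| Section 6.3.1, oral fluid | Day 0; silent on before or after |

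1. **Is the sample post-dose under 6.1.1?** Yes. This does not depend only on reading the bullets as a strict sequence. The step itself places the sample inside the observation period, and the schedule table places that period after the dose.

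2. **Is there another pre-dose oral fluid sample?** No. Sections 6 and 6.3.1 provide for two samples, one at day 0 and one at Visit 2. The allowance for collecting a baseline sample up to 2 months early applies to blood only.

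3. **Which other baselines share the problem?** None. Blood and the initial nasal swab precede the dose in 6.1.1, section 6.3.1 places blood sampling before LAIV, and section 6.4 calls the baseline IgA swab pre-vaccine. The primary outcome uses the swabs from after vaccination.

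4. **Could affected samples be identified later?** Not from what is specified. The 6.1.1 list asks for batch number and expiry but names no sample or dose time, and the labels in section 6.3.2 carry a date only.

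5. **What would an effect do to the planned summaries?** Suppose, as an assumption, that post-dose collection multiplied each child's day 0 reading by the same factor (1 − f).
   - The day 28/day 0 ratio would be multiplied by 1/(1 − f). At f = 0 this is 1 and nothing changes. The documents give no basis for any value of f above 0.
   - On the log scale, each day 0 value would shift by the constant log(1 − f). In the section 9 regression on logged data this changes the intercept and leaves the slope and R-squared as they were. The constant also cancels from the geometric mean ratio between children who shed and children who do not.

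**The case against.** The strongest reply is that the harm is conjectural. The analyte is IgG, and 20 minutes is too short for a vaccine-induced IgG response, so the sample can still serve as an immunological baseline. The vaccine is given as 0.1 ml per nostril (section 5.2), whereas the oral fluid is swabbed from the teeth and gum line (section 6.3.1). Nothing in the documents says that vaccine reaches that site in an amount that matters. The readout is also a supporting one: the secondary objective names HI and/or MN and nasal IgA, and the day 28/day 0 use of oral fluid is inferred from a single line of section 9.1.2. The study is a descriptive pilot that is not powered for significance testing.

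All of this stands, and it limits the weight of the point. It does not remove the contradiction between 6.1.1 and the synopsis and section 1.2, or the difference in conditions between the two samples.

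A reader might go further and infer three things that the documents do not support:

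- **That the oral fluid response is inflated by a definite amount.** No figure for loss of signal is given, and zero is possible.
- **That the association between shedding and immunogenicity is biased.** A common proportional shift leaves the slope, R-squared and between-group ratio unchanged, as shown in step 5. The association would suffer only if the effect varied between children, and nothing in the documents indicates that it does.
- **That all four strains are affected.** Oral fluid testing starts with the H1N1 antigen alone.

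**Conclusion.** The point holds as an internal contradiction with a possible, unquantified consequence for one secondary readout. The timing conflict is certain: section 6.1.1, read with the schedule table, places the day 0 oral fluid sample after the dose, while the synopsis and section 1.2 place it before. The order applies to every participant who follows the list, up to the target of 30. That count refers to sample timing and is not evidence of measurement error in 30 children.

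Any effect on the assay rests on the assumption that vaccine liquid or antigen gets into the oral fluid sample. The documents neither quantify nor exclude this. If it happens, it touches only the day 0 value in the oral fluid day 28/day 0 comparison. The serum, nasal IgA and primary shedding outcomes are not affected. Severity is minor; the case for acting is that the correction is cheap and restores the design that the protocol already states.

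**What to change.** In section 6.1.1, list oral fluid collection before LAIV administration, beside the baseline blood and nasal swab, and remove it from the observation step. State in section 6.3.1 that the day 0 oral fluid sample precedes the dose. Have the CRF record the clock time of the oral fluid sample and of vaccination, so that any child sampled out of order can be identified.

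The cost is an edit to the visit checklist, one clarifying phrase and two CRF time fields. The sample, visit and staff stay the same, and section 6.3.1 puts the collection at around a minute. If any children have already been sampled under the present list, describe their value as day 0, within 20 minutes post-dose, and report it as such.
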